## **B.9. Benefits to the VA**

As a result of Secretary Shinseki's leadership, VHA is prepared to implement the patient aligned care team (PACT)/patient-centered medical home (PCMH) model to coordinate the multiple biopsychosocial needs of patients with chronic illness. There is some evidence that when implemented well, PACT/PCMH can improve quality of care and patient and provider satisfaction. There is a more significant body of literature that indicates interventions and primary care programs designed around models underlying the PACT/PCMH (e.g., Chronic Care Model) are associated with improved patient care processes and outcomes. Further evidence is available that self-management support is likely a necessary, if not in and of itself sufficient, component of PACT/PCMH. The proposed research would examine whether programs aimed at matching resources to patient disease control lead to superior outcomes than simply having booster phone calls in addition to usual care. Answering this question will provide important evidence concerning the overall goal of sustained long-term implementation of the disease management programs as part of PACT/PCMH in the VA and other healthcare systems.

## **C. METHODS**

### **C.1. Overview of Study Design**

**We propose to conduct a two-arm 18-month randomized clinical trial** for veteran patients with pharmaceutically treated hypertension with uncontrolled systolic BP ( $\geq 140$  mmHg for non-diabetic or  $\geq 130$  mmHg for diabetic patients). The primary outcome is degree of improvement in systolic blood pressure. **We seek to enroll until we are able to randomize 400 patients.**

**Intervention Arm (n = 200 patients):** Patients' hypertension control, assessed at baseline, 6, and 12 months, will be used to decide the resource intensity of strategies:

- Medium/level 1 resource intensity: a **registered nurse (RN)** will provide monthly tailored behavioral support telephone calls + home BP monitoring.
- High/level 2 resource intensity: a **pharmacist** will provide monthly tailored behavioral support telephone calls + home BP monitoring + pharmacist-directed medication management.
- Booster (low) resource intensity: a **licensed practical nurse (LPN)** will provide non-tailored behavioral support telephone calls every two months to patients whose systolic blood pressure comes under control

**Control Arm (n = 200 patients):** An LPN will provide non-tailored behavioral support telephone calls every two months (identical to booster (low) resource intensity component of the titrated intervention). The control

arm will utilize the same procedures as the booster (low) intensity level in the intervention arm.

**Table 2: Summary of Study Intervention and Timeline**

TITRATED DISEASE MANAGEMENT SUPPORT (expected patients = 200, program duration of 18 months)	
Individuals randomized to the titrated disease management arm will receive medium/level 1 resource intensity [RN delivered] or high/level 2 [pharmacist delivered] disease management support depending on their level of blood pressure control. Initial assignment will be based on clinic blood pressure results over the past year. At the 6-month and 12-month study visit, disease management program intensity will be reiterated to medium/level 1 or high/level 2 resource intensity levels based on a combination of home, clinic, and study BP levels. Patients who's systolic blood pressure becomes in-control will be placed at a booster resource level [LPN delivered]. There will also be a trigger to increase resource intensity. Resource levels consist of:	
Medium/Level 1 resource intensity – RN-delivered monthly tailored telephone behavioral self-management support calls + Home BP monitoring with feedback to RN nurse educator. Based on preliminary analysis Durham VAMC patients, we expect ~130 of 200 intervention patients in this category at baseline.	
High/Level 2 resource intensity – Pharmacist delivered telephone behavioral self-management support + Home BP monitoring with feedback to pharmacist + Algorithmic medication changes directed by pharmacist (with physician backup). Based on preliminary analysis Durham VAMC patients, we expect ~70 of 200 intervention patients in this category at baseline.	
NOTE: Patients who are considered to be in control at months 6 and/or 12 (systolic BP <140 for non-diabetic and < 130 for diabetic patients)  will be moved to booster resource level [LPN-delivered telephone behavioral self-management support calls delivered approximately every 2 months].	
BOOSTER RESOURCE LEVEL CONTROL (expected patients = 200, program duration of 18 months)	
Booster Level [LPN delivered] – LPN-delivered telephone behavioral self-management support calls delivered approximately every 2 months for 18 months.	

**Table 3: Summary of Differences in Intervention Resource Levels**

Attributes	Resource Level		
	Medium/Level 1	High/Level 2	Low/Booster
Delivered by	RN	Pharmacist (highest paid)	LPN (lowest paid)
Key clinician attributes	
 
Can use clinical judgment to answer clinical questions and provide related assistance to patients
 
Can do clinical nursing assessments
 
	
 
Can prescribe medication
 
Trained in medication management
 
Can provide clinical assessments of patients
 
	
 
Able to follow directions of higher level clinicians per protocol
 
May not do clinical assessments
 

Behavioral call frequency	Monthly	Monthly	Every two months
Modules activated by telephone calls will be tailored to patient	Yes	Yes	No
Clinician trained in motivational interviewing	Yes	Yes	No
Home BP monitoring	Yes	Yes	Not part of intervention
Pharmaceutical management	No	Yes	No

Please note that references to specific roles or individuals who will conduct study procedures are indented to represent roles on the study team, not specific individuals. Roles may be performed by study team members with appropriate license and/or scope of practice. With appropriate changes made to the staff listing, specific individuals in study roles may change during the course of the study.

**C.2. Site**

The study will be conducted among patients receiving primary care at the Durham VAMC, including VA Community Based Outpatient Clinics (CBOC) as appropriate. These venues are staffed by 77 (35.68 FTEE) PCPs who deliver care to over 21,000 unique ambulatory care patients with a diagnosis of hypertension (~10,100 in Durham). The clinics serve a diverse patient population, with approximately 34% African-American

patients. Decisions related to targeting specific Durham VAMC affiliated clinics as part of the enrollment process may be made by the PI.

### **C.3. Patient Identification**

To be enrolled, patients must meet **all inclusion** criteria and have **none of the exclusion** criteria:

#### **C.3.a. Inclusion Criteria Determined by Initial Review of the VA Electronic Health Record (CPRS).**

- Age  $\geq$  18 years
- Assigned PCP in one of the clinics of the Durham VAMC (including CBOCs).
- Had at least 1 primary care visit at the Durham VA or affiliated CBOC in the last year.
- Diagnosis of hypertension requiring medication, as determined by:
  - ICD 401.0, 401.1, or 401.9 for  $\geq$  2 outpatient encounters during the prior year **and**
  - Received a prescription for **at least 1** of the following classes of hypertensive medication in the previous year: 1) ACE inhibitors; 2) alpha blockers; 3) angiotensin II inhibitors; 4) beta blockers; 5) calcium channel blockers; 6) diuretics; 7) antihypertensive combination; and/or 8) antihypertensives, other
- Out of control systolic blood pressure: Durham VAMC (including CBOCs or other affiliated clinics captured in the Durham VAMC electronic health record) outpatient BP measurements  $\geq$  150 mmHg for non-diabetic or  $\geq$  140 mmHg for diabetic patients over the last year. If additional patients need to be approached to be offered the opportunity for further screening, non-diabetic patients with mean outpatient systolic BP of  $\geq$  140 mmHg or diabetic patients with mean outpatient systolic BP of  $\geq$  130 mmHg over the past year may be approached. Systolic BP cutoffs are based on the Seventh Report of the Joint National Commission on Prevention, Detection, Evaluation and Treatment of High Blood Pressure (JNC 7). **Initial screening BP levels have been inflated because of evidence that patients frequently have lower study baseline BPs than would be expected based on the mean of clinic BP results over the last year.**

#### **C.3.b. Inclusion Criteria Determined During Initial Screening Phone Call with Potential Subjects.**

Patients must indicate that they both:

- Have a VA or affiliated clinic provider that they consider to be their main PCP.
- Receive the majority of healthcare at the Durham VAMC (or affiliated clinic).

These inclusion criteria are used to ensure that patients in the trial consider themselves to be VA primary care patients who are receiving hypertension care in the VA. We conceive of this pragmatic trial as informing interventions that would be suggested by the PACT/PCMH model. Key to this model is the integration of patient-responsive services within a care team. Clinicians in this study will have the ability to communicate with the patients care team. This link to primary care differentiates the proposed program and eventual implementation from stand-alone disease management programs that may be provided by outside groups. Our approach is supported, by the PACT/PCMH and the Chronic Care Model. In a 2006 mailed survey of Durham VAMC patients with diabetes that we conducted, 17% respondents reported that they do not have a PCP at the Durham VAMC who provides the majority of their diabetes care. If a patient switches to another VA facility during our study we will no longer conduct monthly or bimonthly encounter calls but we will continue to schedule study follow up visits.

#### **C.3.c. Exclusion Criteria Determined by Initial Review of the VA Electronic Health Record (CPRS).**

- Active diagnosis of psychosis.
- Diagnosis of metastatic cancer.
- Type 1 diabetes
- Class IV congestive heart failure (CHF).
- Currently receiving kidney dialysis or if estimated glomerular filtration rate (eGFR) levels are  $\leq$  15.
- Former, current or pending solid organ or bone marrow transplant patient.
- Chronic obstructive pulmonary disease (COPD) requiring oxygen.
- Resident in nursing home or receiving home healthcare.
- Patient is pregnant.

- At the time of potential enrollment, participating in another ongoing hypertension, diabetes, cholesterol, or cardiovascular disease clinical trial or patient-level hypertension and/or CVD related quality improvement management program that the study investigators consider likely to be a co-intervention.

**C.3.d. Exclusion Criteria Determined During Initial Screening Phone Call with Potential Subjects.**

- Refusal or inability to consent to an in-person baseline visit.
- Planning to leave the area prior to the anticipated end of participation.
- Inability or unwillingness to come to the Durham VAMC for baseline-, 6-, 12-, and 18-month study visits.
- Does not have reasonable access to a telephone.
- Does not speak English.
- Resident in nursing home or receiving home healthcare.
- Severely impaired hearing or speech (Patients must be able to respond to phone calls.)
- Severely impaired vision (Patients must be able to read mailed material).
- At the time of potential enrollment, participating in another ongoing hypertension, diabetes, cholesterol, or cardiovascular disease clinical trial.
- Patient reports currently receiving dialysis (may or may not be at the VA).
- Type 1 diabetes, as reported by the patient.
- Patient indicates she is pregnant or planning to become pregnant in the next two years.
- Patients with class IV CHF, dialysis-requiring renal disease, and type 1 diabetes have blood pressure and/or blood sugar management that are beyond the scope of a primary care pharmacist. Exclusion of patients with COPD requiring oxygen and class IV CHF is done (similar to our exclusion of patients with metastatic cancer) to keep patients with end-stage or near end-stage illness out of the study, both because their life expectancies minimize the importance of hypertension control.

[figure not shown]
**C.3.e. Exclusion Criteria Determined During the Baseline In-Person Visit with Potential Subjects.**

- Refusal or inability to provide informed consent and HIPAA authorization form.
- Arm size > 50 cm
- Unable to obtain (including by arm) valid blood pressure readings
- Inadequate mental status to complete the protocol, as judged by five or more errors on the Short Portable Mental Status Questionnaire (SPMSQ).
- Patients who indicate they have potential to become pregnant (i.e. have not reached menopause (defined as not having a period for one year or more), not had surgical sterilization such as a tubal ligation, or otherwise report they are not able to have children) will be asked to complete a urine pregnancy test (unless they report being pregnant or planning to become pregnant in the next two years). Patients who report being pregnant, planning to become pregnant in the next two years, or have a positive pregnancy test will be excluded from the study before randomization.

**C.3.f. Exclusion Criteria Post Patient Enrollment and Randomization.**

Before any medication management begins by a pharmacist (intervention arm) and at each study visit (control and intervention arms) the pharmacist and/or research-assistant will ask female study subjects who reported during the recruitment process that they could still have children if they are pregnant or plan to become pregnant before the end of the study (time period will vary depending on how far into the intervention the patient has progressed). Patients indicating that they are pregnant or plan to become pregnant will then be disenrolled from the study. If the pharmacist becomes aware of pregnancy during the course of the medication management, the patient may be disenrolled from the study based on the clinical judgment of the pharmacist

**Figure 1. Study Flow**

and study physician (i.e. if the pharmacist and study physician [or appropriately licensed backups] feel that such disenrollment does not put the patient at increased immediate risk). Any disenrolled patients will be referred to their primary care provider for follow-up.

**C.4. Recruitment of Minorities and Women**

Hypertension disproportionately affects African-Americans compared with Whites. Our research team also has a track record of successful minority recruitment. Investigators on this study have conducted numerous clinical trials and other studies that have recruited between 44% and 59% minority patients, primarily African American, at the Durham VAMC and surrounding community.

There will be no inclusion/exclusion criteria based on gender. Approximately 8% of primary care patients at the Durham VAMC are women.

**C.5. Patient Enrollment**

1. Potential subjects will initially be identified based upon VA electronic medical records. First, we will identify

patients with pharmaceutically treated hypertension based on ICD-9 codes from encounters in the last year and pharmacy records using our inclusion/exclusion criteria. Information over the past 365 days will be used to calculate patients' mean SBP and determine the last SBP recorded. Patient eligibility at time of enrollment is based on mean SBP over the past 365 days at the time of the patient pull or subsequent prioritization of who to contact as potential subjects.

2. PCPs at Durham VAMC and at Durham affiliated clinics through which we have not begun recruiting patients for this study will be notified at the monthly PCP meetings (or through other similar venues) that we are recruiting for this study. Recruitment methods will be the same at the Durham VAMC and affiliated clinics if a PCP indicates that she or he does not want her or his assigned patients to be contacted, we will not include them in the study. If the provider wishes to review a list of her or his patients that may be contacted, she or he

will be given 14 days to do so. At the end of 14 days, it will be assumed that the provider approves the list. This procedure provides a link to primary care as suggested by the PACT/PCMH model and provides additional human subjects protection in case a provider believes that the patient is not appropriate for the protocol for some reason that is not evident from the medical record. We will approach eligible patients who have an upcoming appointment at the Durham VA or affiliated clinics. Patients will be mailed letters introducing the study. Patients can call a toll-free number to request not to be contacted by the study team or if they have any questions. Before sending these letters, the study RA and/or study coordinator will review each patient's medical record to determine if they match the patient eligibility and ineligibility criteria as outlined in Section C.3 (Patient Identification). This process will be repeated on a rolling basis throughout the study recruitment period. This basic process for recruiting patients has been successfully used in other clinical trials conducted at the Durham HSR&D Center of Excellence.

3. Unless the patient contacts the study team to decline participation, the RA (or other authorized study staff member) may contact the patient by telephone to explain the study, ask screening questions concerning eligibility, and arrange an in-person meeting at the clinic to further describe the study, obtain informed consent, and interview the patient. During the phone call, the RA will remind patients to take medication as prescribed by their doctor. A similar reminder phone call will be made approximately a day (may be a business day) prior to the baseline and subsequent study data collection visits.

4. The baseline interview includes demographics and assesses patients' health behavior, social and medical environment, and interactions with their provider. Patients will also have baseline BP, height, weight, and pulse measurements obtained. Patients that have to end the baseline appointment early may finish the behavior and social assessment over the phone or come back to the VA to complete it in person.

5. All patients will be followed for 18 months. Trained personnel, masked to study arm assignment (if possible), will obtain the patients' outcome values (e.g., BP) and covariates at baseline, 6, 12, and 18 months using a digital sphygmomanometer and digital scale according to a standard protocol (submitted separately to the Durham VAMC IRB) [Approved June 14, 2012].

6. All study measures assume physical capability of patient to have study measures taken (e.g. if patient is an amputee certain measurements such as blood pressure or weight may not be taken) within the constraint of the location of the study visit. In addition a patient can refuse to complete any study measure. We will only exclude if the patient based on this item if we are unable to obtain valid blood pressure measurements.

## **C.6. Randomization**

1. Once a patient has consented and completed the measurement battery, the patient will be randomized to one of the 2 study arms.

2. We will stratify randomization by diabetes status (because of differing hypertension treatment goals) and baseline SBP [SBP Low Strata = < 150mmHg and High Strata = SBP ≥ 150 mmHg for non-diabetic patients and Low Strata = SBP < 140mmHg and High Strata = SBP ≥ 140 mmHg for diabetic patients]. Diabetes is defined as having both: ICD 250.xx on ≥ 2 outpatient encounters during the prior year and prescription for oral hypoglycemic medication (e.g., sulfonylurea, metformin, thiazolidinedione, secretagogues, acarbose) and/or insulin during the past year. Data for the diabetes status variables will come from the data pull for evaluating inclusion/exclusion criteria and SBP is an average of study assessed readings at baseline.

3. Randomization will occur within the study computerized database. As a backup, randomization assignments by strata may be placed in sealed, consecutively numbered envelopes by a masters-level statistician before patient enrollment begins. Other similar systems for randomization, developed in consultation with study statisticians, may also be used as backup.

4. We will use blocked randomization; to prevent contamination, research assistants will be blinded to block size.

5. Patients will be told the arm to which they are assigned by the RA (or other appropriate study staff member) at the enrollment study visit. If the patient must leave the study appointment after informed consent and HIPAA Authorization have been obtained, but before randomization, the arm assignment will be revealed to the patient over the phone.

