### **C.7. Blinding of Study Personnel**

Reasonable attempts will be made to divide study personnel into two groups for the purpose of follow-up outcomes assessment: those involved with follow-up data collection and those delivering the intervention. If possible, personnel responsible for follow-up data collection will be blinded to patients' group assignment. Baseline data collection will be done before any staff members know of study arm assignment. Drs. [name] and [name] (or his appropriately licensed back-up/replacement) may have to respond to patient inquiries or adverse events, so they cannot be blinded. However, the research assistant (RA), and Drs. [name] and [name] (Co-Is) will be blinded throughout the study (unless conduct of the study requires blinding to be broken for any given member of the study team). The blinded study team will be responsible for all scientific judgments where knowledge of arm assignment could bias the person making the judgment. This model has worked in our previous studies.

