#### **C.9.d. Process for determining and communicating changes in titrated resource levels.**

After completing each study visit, the interventionist to whom a patient is assigned (or other authorized unblinded study staff member if back-up is required) will access all eligible BP values for which the titration

determination will be made. BP readings will come from the following sources: 1) clinic BPs extracted nightly from the Durham VistA system (process that has been arranged by the PI for use in the HTN-IMPROVE study); 2) study BPs entered by the research assistant; and 3) home BPs reported during planned study calls. **A combined mean of these BP measurements will be calculated to produce information on the cut points upon which titration will be based.** Because measurements will have already been entered into the intervention software, the calculation will be automated. The interventionist (or other authorized unblinded study staff member if back-up is required) will inform the patient if any changes in resource intensity are indicated. The intervention software will record all titrated changes in resource intensity.

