## C.22. Data Quality

Use of the electronic data management system, described in section J.1 below, will aid the research assistant (RA) conducting study visit to monitor which data collection instruments and questions have been completed by the patient. Though the computerized auditing procedure, the RA will determine if all questions have been answered. If not, the subject will be given the opportunity to answer questions. As with all study components, the study patient will have the opportunity to decline to answer any questions. Before the end of the study visit, the RA will complete a checklist to ensure that all measurements are completed.

Study implementation and quality assurance methods that we will be employed include: 1) careful scheduling and thorough, timely monitoring of the planned visit schedule to be certain that complete visits do occur; 2) collection of contact information for each participant at each visit; 3) prompt contact and rescheduling of missed study visits; and 4) review and documentation of the reasons for missed visits that do occur. We will also review individual patient data promptly to identify problems or missing values that can be completed by follow-up.

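### Protocol C.6 item 5 makes the research assistant the default person to tell patients their arm, although C.7 lists that role as blinded throughout the study

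*Protocol*

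**What the plan says.** **Who reveals the arm.** C.6, item 5: "Patients will be told the arm to which they are assigned by the RA (or other appropriate study staff member"). This happens at the enrollment visit. If the patient has to leave after consent but before randomization, the arm is revealed by phone, and no role is named for that call.

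**Who is blinded.** C.7 names the RA and two co-investigators as staff who "will be blinded throughout the study (unless conduct of the study requires blinding to be broken for any given member of the study team"). It makes this blinded group responsible for scientific judgments that knowledge of the arm could bias.

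**Assessor masking.** C.7 promises reasonable attempts to split staff into two groups, "those involved with follow-up data collection and those delivering the intervention". It then adds "If possible, personnel responsible for follow-up data collection will be blinded" to assignment. C.5, item 5, is similar: "Trained personnel, masked to study arm assignment (if possible), will obtain" outcome values at baseline, 6, 12 and 18 months.

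**What the RA does at study visits.** C.22 describes the RA as conducting the visit and says "Before the end of the study visit, the RA will complete a checklist to ensure that all measurements are completed". C.9.d lists "study BPs entered by the research assistant" among the sources for titration. C.3.f says that "at each study visit (control and intervention arms) the pharmacist and/or research-assistant will ask female study subjects" about pregnancy, limited to those who had reported that they could still have children.

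**The concern.** Someone who tells a patient the arm is no longer blinded to that patient. C.6 gives this task, by default and for every randomized patient, to a role that C.7 describes as blinded for the whole study. The same role is present at study visits and handles the primary-outcome data.

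Patients know their arm in this trial, so masked assessment is one of the remaining protections for the primary outcome, systolic blood pressure (SBP) at follow-up visits. A default that works against that masking opens an avoidable route to assessor knowledge. It also weakens C.7's assurance that blinded staff make the judgments open to bias.

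**Working it through.** No statistical formula applies, because the point depends on no effect size, SD, power or error rate. The check is a comparison of sections, followed by a count of the outer limit.

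**1. Does the C.6 default conflict with C.7?** C.6 item 5 names the RA first. C.7 blinds the RA throughout. If staff follow the default, the RA knows the arm of each patient told. The default and the blinding statement cannot both hold for those patients unless an exception applies.

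**2. Does C.7's exception cover it?** The exception applies when conduct of the study requires blinding to be broken. Disclosure happens for every patient, so reading the exception to cover it would leave nothing of the rule for the RA. Nor is the RA required for the task, since C.6 itself offers another staff member.

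**3. Can staff comply with both sections?** Yes, by using C.6's alternative discloser. Nothing makes that the normal route, and for disclosure by phone no role is given.

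**4. Do the assessor-masking rules close the gap?** In part. C.7's two-group split separates data collectors from those who deliver the intervention, and telling a patient the arm is not clearly delivery. But C.7's next sentence and C.5 item 5 ask for masked assessors whatever the source of their knowledge. Both are conditional, so they steer a discloser away from that patient's follow-up reading without excluding it.

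**5. Is the RA the person who measures SBP?** The protocol does not say. C.5 refers to trained personnel, C.18 to study personnel, and J.1.b to an authorized staff member. C.22 and C.9.d place the RA at visits and in data entry, which is close to the measurement but is not the measurement. C.5 mentions a separate measurement procedure sent to the IRB. It is not at hand and may name the assessor.

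**6. Outer limit of exposure.** Inputs: 400 randomized and 15% attrition by 18 months (D.3); follow-up visits at 6, 12 and 18 months (C.18).

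- Scheduled follow-up SBP assessments: 400 × 3 = 1,200.
- Patients expected at month 18, where D.2 tests the treatment difference: 400 × (1 − 0.15) = 340.

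These are all scheduled or expected assessments, not affected ones. The number taken by the person who revealed the arm could be anything from none to all.

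**The case against.** The strongest reply is that the two sections do not strictly contradict each other. C.6 allows someone else to disclose, C.7 has an exception, and both C.5 and C.7 already ask for masked assessors where possible. The note under Table 3 says that role names stand for roles and not individuals, and C.6 item 4 refers to research assistants in the plural. The RA who reveals an arm need not be the one at that patient's later visits. Several features also limit any bias:

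- a digital device, with trained and certified staff;
- the average of three readings;
- baseline data collected before any staff know the arm;
- a gap of at least four months before the first follow-up visit (C.18 window), by which time the discloser may not recall the arm.

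Patients can also reveal their arm to any assessor, so complete masking was never assured.

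All of this stands, and it limits the point to a badly chosen default. It does not remove the point, because the protocol still names as first choice the role it wants blinded.

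A reader might infer more: that an unblinded RA measures the primary outcome, that nothing in the protocol protects assessor masking, or that all 1,200 follow-up readings are compromised. The documents support none of these. No section names the RA as measurer, two sections ask for masking, and 1,200 is simply the full visit schedule. A reader might also take C.9.b as a firm rule separating messenger from assessor. It says only that an unblinded team member tells intervention patients of intensity changes, and does not bar that person from measuring blood pressure.

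**Conclusion.** The point holds as an avoidable conflict between C.6's default and C.7's blinding of the RA. It is worth correcting because the remedy is cheap and concerns protection of the primary outcome. It is not evidence that the SBP comparison is biased. The protocol gives no figure for assessor bias and does not identify who takes each reading, so neither the size nor the frequency of any effect can be estimated, and the safeguards listed above probably keep it limited.

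The conclusion assumes that staff would ordinarily follow the default C.6 names. It would lose most of its force if the separate measurement procedure assigns follow-up readings to staff who never disclose allocation, though the wording of C.6 and C.7 would still need to be reconciled.

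**What to change.** Reword C.6 item 5 so that the arm is revealed, in person or by phone, by an existing unblinded staff member who collects no follow-up outcomes, for example the assigned interventionist. Name that role for the phone route as well, and drop the RA as default. Align C.7 by stating that the RA takes no part in disclosure. For this to work, the allocation result has to be shown to the discloser and not to the RA. C.6 item 3 places randomization in the study database without saying who sees the result, so one clause there would help.

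The cost is protocol wording plus minor scheduling: an unblinded staff member must be available, in person or by phone, at the end of enrollment visits, including any at affiliated clinics. An alternative is to bar the discloser from measuring that patient at follow-up, but this could need additional assessors, so it is second choice.

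Optionally, add one field at each follow-up visit recording whether the assessor knew the arm. This does not resolve the wording, but it would show how far masking was kept.
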